For this human subjects study, we will elicit patient preferences toward various treatment outcomes using a participatory ranking exercise and use these rankings to generate individually weighted composite outcomes. These composite outcomes (without any linked participant information) will be used for analyses within OLDW that will estimate patient-centered treatment effects of four different classes of second-line medications for Type 2 diabetes with respect to those composite outcomes specifically. The four drug classes that will be examined

are the GLP-1 receptor agonists (GLP-1RA), SGLT2 inhibitors (SGLT2i), DPP-4 inhibitors (DPP-4i), and sulfonylureas (SU).

Background (Include relevant experience, gaps in current knowledge, preliminary data, etc.):

Type 2 diabetes (T2D) is one of the most common and serious chronic health conditions in the U.S.¹ Optimal patient-centered T2D care is predicated on treating each patient with medications that are likely to yield the most benefit and risk the least harm, weighing the best available evidence against each patient's preferences and situation. While metformin is consistently recommended as the 1st-line drug in the management of T2D, there is less clarity regarding 2nd-line therapy as new drug classes were approved and introduced into practice,²⁻⁵ resulting in decisional dilemmas for patients and clinicians, and potential missed opportunities to select the drug that best optimizes the patient's health.

Cardiovascular disease (CVD), heart failure (HF), and chronic kidney disease (CKD) are leading causes of morbidity, mortality, and costs associated with T2D.⁶⁻⁹ Randomized controlled trials (RCTs) designed to evaluate the CV safety of T2D drugs revealed additional therapeutic benefits of glucagon-like peptide-1 receptor agonists (GLP-1RA) and sodium-glucose cotransporter 2 inhibitors (SGLT2i) with respect to CVD, HF, and CKD outcomes among patients at high risk for these events. However, it is unknown how each patient's preferences and values impact the comparative effectiveness of these drugs.

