As a result, patients and clinicians face a decisional dilemma at the heart of T2D management: *Which drug class would be best for the specific set of outcomes desired by an individual patient with T2D?* Addressing these knowledge gaps is critical for patients and clinicians to engage in shared decision-making; for professional societies to develop guidelines that reflect scientific evidence and patient priorities; and for health systems and payers to make formulary decisions.

Study Design and Methods

Methods: Describe in lay terms, completely detailing the research activities that will be conducted by Mayo Clinic staff under this protocol.

We will ask a purposive sample of patients with T2D (N=25) to engage in a participatory ranking exercise in which they will rank the outcomes of T2D therapy are most important to them personally and then contextualize these decisions. Participatory ranking exercises are widely used in studies of preference elicitation to determine the relative importance of treatment attributes and outcomes.¹⁰ We will develop an inventory of potential outcomes and adverse events associated with the four drug classes of interest (e.g., hospitalization, severe hypoglycemia). As part of an individual interview with a member of the research team, we will ask patient participants to rank these pre-specified outcomes in order of their relative personal importance using a secure online survey platform (Qualtrics). The researcher will ask patients to contextualize their ranking decisions. Next, participants will be asked to identify additional outcomes that are missing from this prespecified list of clinical outcomes, but which may be important to patients with T2D (e.g., medication cost, frequency of administration). Finally, participants will be asked to incorporate these additional, patient-generated outcomes into their ranking decisions and explain their rationale to the researcher.

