Quantitative analysis of the participatory ranking exercise: Each participant's responses will be used to generate an individualized weighted composite outcome. We will consider a utility function that is a weighted combination of the individual endpoints specified by each participant, with weights determined by the patient's preferences as proposed in Butler et al.¹⁶ The patient's preference weights will be scaled to sum to 1, such that the patient-specific outcome will be a convex combination of the eligible outcomes. With the weighted utility function, we then define potentially counterfactual treatment effects, defined as the expected utility function under the four different treatment exposures. The optimal individual treatment rule is defined as in Qian and Murphy¹⁷ as the treatment that maximizes the expected utility function.

We will then use the composite outcomes generated using the participator ranking exercise (see above) in a study that uses de-identified data within OLDW. Specifically, we will emulate a target trial comparing the effectiveness of GLP1-RA, SGLT2i, DPP-4i, and SU classes with respect to each of these patient-specified composite outcomes. The target parameter will be the six pairwise differences in the personalized utility function between the drug classes. We provide an overview of that analysis below, though all analyses using

OLDW data have been previously deemed exempt from IRB review as all data is statistically de-identified by OptumLabs prior to being made available to researchers.

Primary analyses will be conducted under an intention-to-treat approach, modified to define “intention” as a patient having two consecutive fills of the assigned drug. All patients will continue follow-up and complete all outcome assessments until the planned conclusion of the study or end of observation in OLDW.

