We will estimate multinomial propensity score models using data from 12 months prior to the index date to account for the multiple treatments.¹⁸ Predictions from the estimated propensity score model can be used for inverse probability weighting (IPW) to emulate baseline randomization. We will allow for flexible modeling strategies with controls to assess for overfitting. Our proposal is to use the super learner framework¹⁹ with a diverse set of individual prediction algorithms included in the ensemble. The super learner framework allows for flexible estimation of an ensemble predictor with the theoretical properties of cross-validation for model selection to control for overfitting. The framework has been demonstrated to outperform individual algorithms for the estimation of propensity scores.^{20,21} The distribution of the predicted propensity scores will be evaluated for evidence of violations of the positivity assumption. For moderate violations of positivity, the propensity scores will be truncated at 0.01 and 0.99 to control inflation of the standard errors. Our intention is to use the entire distribution of OLDW as our population of interest, but if more extreme positivity violations are observed, the reference population will be narrowed to a realistic treatment intervention population.

The proposed IPW weight with multinomial treatment groups is unstabilized, as our primary estimand is the population average treatment effect.²² If weights have extreme values when evaluating the distributions, then the stabilized version using the denominator proposed in Yoshida²³ for the optimal matching stabilized weights with multiple treatments will be used as a sensitivity analysis to avoid large confidence intervals for the effect estimates. The final propensity scores will then be incorporated as IPWs into a time-to-event model. If the proportional hazards assumptions hold, this will be a Cox model; otherwise, we will use Akaike Information Criteria to identify the best parametric time-to-event specification for the data. For the final model, we will report model diagnostic and performance statistics, and either hazard or time ratios with 95% confidence intervals. A single model with all treatment groups will be estimated and the omnibus test for at least one treatment group having a different cumulative incidence rate will be evaluated. If that test is statistically significant, then each pairwise comparison will be tested and pairwise effects estimated.

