The targeted learning algorithm for the causal hazard rate as defined in Moore and van der Laan²⁴ will be implemented to estimate the four treatment hazard rates and the corresponding hazard ratios or time ratios, according to the model specification, will be estimated for each of the 6 pairwise comparisons between treatment groups. A single overall omnibus test for the four hazard rates being equal to each other versus at least one different will be conducted at the 0.05 significance level, with pairwise comparison p-values adjusted using the Holm closed sequential multiple testing procedure.^{25,26}

Predefined subgroup analyses for heterogeneity of treatment effects (HTE) will be evaluated for the following characteristics: sex (female vs. male), race/ethnicity (Black, Hispanic, Asian, other vs. White), and age (45-64, 65-74, ≥ 75 vs. <45 years). While there is no definitive evidence of HTE by these characteristics, the incidence of CVD and kidney disease outcomes are known to vary²⁷⁻³⁰ and may be mediated by different responses to therapeutic interventions. We will also assess for HTE as a function of different levels of underlying CVD risk, as the examined drugs may be more effective at reducing the risks of primary and secondary endpoints among patients at higher risk for these events or with certain CVD risk factors already present.^{31-35 36-39} The primary model will be used to estimate treatment effects across subgroups, with the targeted parameter for the subgroup analysis being the difference in the predicted treatment effect for each pairwise comparison between the

subgroups.⁴⁰ We will estimate multivariable effect prediction models^{41,42} to assess for HTE between the predefined subgroups by incorporating specific parameters for the statistical interaction effect between the treatment and subgroup variables.^{36,37} Propensity score weights will be used to emulate randomization according to the target trial framework. Internal cross-validation will be used to control for overfitting of the prediction model.⁴³ Adjustment for multiple testing will be done accounting for the total number of predefined HTE analyses.

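### The plan's target, six utility differences per composite, has no interval on its own scale, and no planned analysis would support a statement that preferences change the class comparison

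*Combined protocol and SAP*

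**What the plan says.** All references are to the combined protocol and SAP. In the Data Analysis Plan, under the quantitative analysis of the ranking exercise, each participant's weights are scaled to sum to 1 and define a utility. The optimal rule is defined "as the treatment that maximizes the expected utility function". For the OLDW analysis of each composite, "The target parameter will be the six pairwise differences in the personalized utility function between the drug classes".

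Inference comes later in the same section, on another scale. The weighted time-to-event model will report "either hazard or time ratios with 95% confidence intervals". An omnibus test of cumulative incidence must be significant before pairs are tested. The next paragraph describes "A single overall omnibus test for the four hazard rates being equal to each other versus at least one different", at the 0.05 level, with Holm-adjusted pairwise p-values. For sex, race/ethnicity, age and underlying CVD risk the plan also compares effects between groups, with the "targeted parameter for the subgroup analysis being the difference in the predicted treatment effect for each pairwise comparison" between subgroups.

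The Background asks "Which drug class would be best for the specific set of outcomes desired by an individual patient with T2D" and says it is not known how a patient's "preferences and values impact the comparative effectiveness of these drugs". The OLDW text is introduced as an overview.

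**The concern.** Three things do not meet.

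- **Scale.** The target is a difference in expected utility. A hazard ratio or time ratio for a composite is a different quantity, and its interval does not convert to an interval for a utility difference without a further step that the plan does not give.
- **Selection.** The optimal class is a maximizer. Nothing says how its uncertainty is expressed, or whether it is named only after the omnibus and pairwise tests.
- **Comparison.** Every composite is evaluated on the same OLDW data; composites differ in their weights and chosen outcomes. When classes are close, one set of estimation errors under different weights can produce different maximizers, which a reader could take as preferences changing the best class. Reading separate results side by side does not resolve this, because significance in one composite and not in another is not a test of the difference between them.

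At stake is the interpretation of the question that the Background poses.

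**Working it through.** **Figures in the plan.** The plan states no power, effect size or event rate for this analysis, and N = 25 rests on saturation, so there is no sample-size figure to reproduce. The one count that can be checked is right: 4 × 3 / 2 = 6 pairs.

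**What has an interval or test**

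| Quantity | Planned inference |
|---|---|
| Hazard or time ratios, one composite | 95% intervals, Holm-adjusted pairwise tests |
| Equality of four hazard or incidence rates, one composite | omnibus test at 0.05 |
| Class effects between patient subgroups | contrast, adjusted for multiplicity |
| Six utility differences (the target) | none stated |
| Maximizer of expected utility | none stated |
| Class contrasts between composites | none stated |

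**How much this could matter.** The following inputs are assumptions, because the documents do not give them: 8 outcomes shared by all; 25 random rankings; rank-order-centroid, rank-sum or reciprocal weights; normal errors with equal standard errors; correlation ρ between endpoint errors from 0 to 0.9; and the same class contrasts on every endpoint, so no preference effect exists.

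- Utility of class c for participant i: U(i,c) = Σ w(i,k) θ(k,c).
- Standard error of one class utility, with unit endpoint error: s = √[(1 − ρ) Σ w² + ρ]. The SE of a difference is s√2, and leads are stated in that unit.
- Omnibus gate: Σ (U(i,c) − mean)² / s² against the 95th percentile of chi-square with 4 − 1 = 3 df.
- Stand-in for Holm on best versus second: two-sided 0.05/6 = 0.0083, z = 2.64.

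The gate and pairwise test are applied on the utility scale, as a proxy for the plan's hazard-scale tests. Ranges are over weightings and ρ.

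| Truth | Two or more best classes, plain maximizer | Same, after omnibus gate | Separated for some composites, not others (gate plus pairwise test) |
|---|---|---|---|
| Four equal | 14-95% | 0.3-7% | not tabulated |
| Two tied for best | 8-80% | 8-80% | not tabulated |
| One best by 2 SE | 3-32% | 0.6-9% | 3-37% |
| One best by 3 SE | 0.2-4% | no higher than ungated | 8-81% |

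With the gate and the pairwise test together, no run produced two composites with different separated best classes. The last column is large at 3 SE because the lead sits near the cutoff of 2.64, so small differences in weights push some composites over it and not others.

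**Hand check.** For two composites and two equal classes, P(different best) = arccos(r)/π, where r is the correlation between their class differences. With 6 outcomes and rank-sum weights the mean r is 0.81: arccos(0.81)/π = 0.627/3.142 = 0.20. Simulation gives 19.5%.

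**Does a direct contrast work?** In that same setting, take (U(i,A) − U(i,B)) − (U(j,A) − U(j,B)) with its SE from the joint covariance. It rejects in 4.9% of runs, against a nominal 5%. A joint Wald test across all composites with 8 outcomes has (8 − 1) × (4 − 1) = 21 df and rejects in 4-6% of null runs.

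**The case against.** The strongest reply is that the plan already contains a gate. Pairs are tested only after a significant omnibus test, and then with Holm. Read that way, false disagreement largely disappears when all four classes are equal. This stands, and it is why gated and ungated figures appear together. Two limits remain. The plan does not tie the maximizer to those tests, and the gate does nothing when two classes tie for best, because the omnibus test then nearly always rejects.

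A reader might infer that the plan will announce a best class for each participant and so report spurious preference effects in up to 95% of studies. The documents do not support that. They define the optimum as a population quantity, which is sound, and nowhere commit to reporting an estimated best class per participant. The stated hypothesis is only that preferences differ.

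It can also be said that the subgroup analysis is a loose precedent. This is right: it compares one outcome between different patients, whereas composites are different outcomes in the same patients. That is why a joint variance is needed.

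Finally, the simulation is stylized. Participants may add their own outcomes, and the Background expects class-specific benefits. The percentages therefore illustrate size and do not predict it. The missing interval does not depend on them.

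**Conclusion.** The point holds in a limited form. As written, the target parameter has no interval on its own scale, the maximizer is not linked to any test, and nothing planned would support a statement that preferences alter the class comparison. Uncertainty is not wholly absent: the ratio-scale intervals and Holm tests inform comparisons within one composite.

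The consequence is confined to close calls. Under the assumptions above, the plain maximizer is right for 94% of composites at a 2 SE lead and 99.6% at 3 SE. What survives even the strictest reading of the plan is the side-by-side problem: about 3-37% of studies at 2 SE and 8-81% at 3 SE would show separation for some composites and not others, with no preference effect at all.

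A reader might also infer that participants could be steered to a wrong drug. The documents do not support this: composites go to OLDW "without any linked participant information", and in an exact tie either class is a correct maximizer. The harm is one of interpretation. Because the OLDW text is only an overview, a fuller plan may already close the gap; none is cited.

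**What to change.** 1. For each composite, report the six utility differences with 95% intervals, from influence curves or a bootstrap.
2. If a best class is named, give its utility difference from the second-best class with the interval, and describe it as *not separated* when the interval includes zero.
3. If the report says that preferences change the comparison, base this on the difference in class contrasts between composites, with a joint variance from the shared OLDW data. Do not base it on separate per-composite significance.
4. If a fuller OLDW plan already covers these items, cite it.

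**Cost.** A few sentences and modest programming, with no new data. Some composites will have no separated class even when one is truly best. With a cutoff of 2.062 SE for best versus second, about 23%, 65% and 93% of composites are separated at leads of 2, 3 and 4 SE; a plain 95% interval (cutoff 1.96) would separate slightly more. The point estimate of the best class can still be shown.

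The joint test has limited power for small preference effects. Suppose one class is better on four of the 8 outcomes and another on the other four, by δ SE of the difference. The noncentrality is then 8δ²/(1 − ρ). For δ = 1 this is 8 at ρ = 0 (power 31%) and 8/0.4 = 20 at ρ = 0.6 (power 77%). For δ = 2 it is at least 32 (power 96% or more).

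### The stated target is six differences in preference-weighted expected utility, but the analysis overview reports and tests hazard-scale quantities and gives no step from one to the other

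*Combined protocol and SAP*

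**What the plan says.** All references are to the combined protocol and SAP.

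- **Research Question and Aims.** The participants' composites are to be carried into the OptumLabs claims data (OLDW) to "estimate patient-centered treatment effects of four different classes of second-line medications for Type 2 diabetes with respect to those composite outcomes specifically".
- **Study Design and Methods.** Participants "rank these pre-specified outcomes in order of their relative personal importance", then add outcomes of their own and rank again. The data collected are ranks.
- **Data Analysis Plan, quantitative analysis of the ranking exercise.** Weights are derived from preferences by a cited method and scaled to sum to 1, "such that the patient-specific outcome will be a convex combination of the eligible outcomes". The treatment effect is expected utility under each of four exposures, and the optimal rule is defined "as the treatment that maximizes the expected utility function". The estimand is explicit: "The target parameter will be the six pairwise differences in the personalized utility function between the drug classes". The classes are to be compared "with respect to each of these patient-specified composite outcomes".
- **Same section, claims analysis.** This is introduced with "We provide an overview of that analysis below". Follow-up runs "until the planned conclusion of the study or end of observation in OLDW". Inverse probability weights enter a Cox model or, if hazards are not proportional, a parametric model chosen by Akaike criterion. The output is hazard or time ratios with 95% intervals. One sentence words the omnibus test on cumulative incidence. A later one words it as equality of four hazard rates at the 0.05 level, with Holm adjustment of the pairwise p-values. Targeted learning is aimed at the four hazard rates and the ratios for the six pairs.

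Utility is not mentioned again once the claims overview has begun its account of follow-up, weighting and modelling.

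**The concern.** The estimand is additive, participant-specific and weighted. The named estimators and tests are on the hazard, ratio or cumulative-incidence scale, and the text does not say how a participant's weights enter them.

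Three links are missing:

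1. **Which event is modelled.** If two endpoints are coded as occurred or not and weighted 0.8 and 0.2, their weighted sum takes the values 0, 0.2, 0.8 and 1. That variable has no single event time, so a Cox model cannot be fitted to it without a further definition.
2. **The horizon.** Expected utility built from events depends on when it is evaluated. Follow-up to study end or end of observation does not fix that time.
3. **The inference.** No estimator, interval or test is given for the utility difference, and no rule says how the utility-maximizing class is identified from the fitted models.

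At stake is the purpose of the ranking exercise. If the obvious default is used, an unweighted time to first event, participants who list the same endpoints with opposite priorities get the same answer.

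**Working it through.** **Step 1. The plan's own figure.** Four classes give 4 × 3 / 2 = 6 pairs, which matches the six stated. The first Holm threshold within one family of six is 0.05 / 6 = 0.0083. The count is not in dispute, only the quantity compared.

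**Step 2. Target against output.**

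| Item | Stated target | Claims overview |
|---|---|---|
| Quantity | Difference in expected weighted utility | Hazard rates; hazard or time ratios |
| Role of weights | Sum to 1, specific to the participant | Not stated |
| Time point | None given | Follow-up to study end or end of observation |
| Omnibus test | None on utility | Cumulative incidence in one place, hazard rates in another |
| Pairwise inference | None on utility | Ratios with 95% intervals; Holm p-values |

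The subgroup paragraph targets a difference in predicted treatment effect but names no scale. The as-treated paragraph adds reweighting for censoring and no new effect measure. Neither supplies the missing link.

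**Step 3. Can the two scales disagree?** The documents give no event rates, so every input here is assumed. Take two independent endpoints with constant yearly hazards: class A 0.02 and 0.12, class B 0.04 and 0.08. Let utility be the weighted probability of being free of each endpoint at 3 years:

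U(a) = w × exp(-3h1) + (1 - w) × exp(-3h2)

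- Endpoint 1: exp(-0.06) - exp(-0.12) = 0.9418 - 0.8869 = +0.0548 from unrounded values, favouring A.
- Endpoint 2: exp(-0.36) - exp(-0.24) = 0.6977 - 0.7866 = -0.0890, favouring B.
- Unweighted first-event hazard ratio, A against B: (0.02 + 0.12) / (0.04 + 0.08) = 1.167, favouring B. It contains no w.
- U(A) - U(B) = 0.0548w - 0.0890(1 - w).

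| Weight on endpoint 1 | First-event hazard ratio | U(A) - U(B) | Class with higher utility |
|---|---|---|---|
| 0.9 | 1.167 | +0.040 | A |
| 0.7 | 1.167 | +0.012 | A |
| 0.5 | 1.167 | -0.017 | B |
| 0.3 | 1.167 | -0.046 | B |
| 0.1 | 1.167 | -0.075 | B |

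The sign changes at w = 0.0890 / (0.0548 + 0.0890) = 0.62. Above that weight the ratio favours B while the participant's own utility favours A.

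**Step 4. A ratio does not by itself fix a difference.** With risk in the comparison class 1 - (1 - p)^0.80, an assumed hazard ratio of 0.80 gives absolute risk differences of 0.4, 1.0, 1.9, 3.7 and 6.5 percentage points at baseline risks of 2%, 5%, 10%, 20% and 40%.

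**Step 5. Role of the horizon.** In the Step 3 example with w = 0.7, U(A) - U(B) is 0.7 × 0.0194 - 0.3 × 0.0362 = +0.003 at 1 year, +0.012 at 3 years and 0.7 × 0.0861 - 0.3 × 0.1215 = +0.024 at 5 years. At this weight the horizon changes the size and not the sign, but without one there is no number to report.

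**The case against.** The strongest reply is about scope. This is a minimal-risk protocol for a ranking and interview study of 25 people. The claims work is exempt from IRB review, and the text calls itself an overview of one component of a broader study. A fuller plan may hold the missing step. That stands as a caution and is why a citation would be an acceptable answer. It does not remove the point. The overview is detailed enough to give truncation limits, an alpha level, a multiplicity procedure and a model-selection criterion, yet it gives no estimator for its own declared target.

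A second reply is that the plan is not limited to ratios. It estimates four class-level hazard rates and mentions cumulative incidence, from which absolute risks could be built. That is correct, and it makes the remedy cheap. But the conversion is not written, and the tests stay on the other scale.

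A reader might infer more than the documents support:

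- **That analysts could reverse a participant's preferred class by their choice of baseline risk or horizon.** Baseline risk is a fact the claims data would supply, not a choice. Step 5 does not show a reversal by horizon.
- **That the rank-to-weight conversion is left open.** The plan assigns the weights to a cited method that cannot be seen here. The fair statement is that the rule is not restated.
- **That the first-event ratio in Step 3 is what will be fitted.** The plan does not say. A weighted event definition could behave differently.

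**Conclusion.** The concern holds in this form: the quantity the overview reports and tests is not the stated target, and the text does not produce the utility-maximizing class. This is more than missing detail, because the omnibus test, the Holm adjustment and the confidence intervals are all explicitly attached to another scale. It should be fixed before the claims analysis is run.

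Confidence is high that the step is absent from these documents and lower on its practical consequence. The illustration (hazard ratio 1.167 throughout, utility difference +0.040 to -0.075) rests on assumed constant hazards, independent endpoints, a 3-year horizon and an unweighted first-event composite. It shows that the scales can disagree in direction, not how often or by how much they will. The documents do not support saying that the utility analysis cannot be done, or that no fuller plan exists.

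**What to change.** Make the utility difference the primary reported and tested quantity:

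1. Prespecify one horizon.
2. At that horizon, use the planned weighting or targeted-learning machinery to estimate each component's counterfactual mean or risk under each class.
3. Combine these with the participant's weights into U(a), coded so that higher is better, and name the class with the largest U(a).
4. Report the six differences with influence-curve or bootstrap 95% intervals.
5. Move the omnibus test and Holm adjustment to this scale, and keep hazard or time ratios as secondary.
6. Write out how ranks become weights, which outcomes are eligible, and how death is handled. The choice of coding is for the study team.

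If a fuller OLDW plan already contains these steps, a citation in the Data Analysis Plan is enough. Restating the target as a ratio would also restore consistency, but the optimal rule and the stated aim would then need rewording, since both rest on utility.

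The cost is plan wording and some extra programming on the same data and propensity scores. Component risks are estimated once and reused for every participant. The real downside is that a horizon must be fixed and later events leave the primary analysis. The sample size of 25 does not change.
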